4.0 Study Design: We propose a multi-site, randomized, double blind, placebo controlled study of 200 patients with decompensated heart failure receiving treatment with IV diuretics for volume overload. Participants will be enrolled at Yale New Haven Hospital and St. Francis hospital. This study was designed to be more pragmatic than the outpatient study (HIC2000022016) proposed in a separate protocol, with a parallel group randomization to 7 days of therapy with either 115 mmol/day of lysine chloride or placebo. 115 mmol/day of lysine chloride was chosen as this represents a similar cumulative chloride load to the higher dose 5-day inpatient study (separate HIC application). The primary endpoint will be the change in blood volume from baseline to 7 days (the range of days may vary between 5-8 days to minimize missing data).

Due to the current pandemic of COVID-19 (SARS-CoV2) and to remain in place for the future, the number of days between the V1 and V2 may be shortened (less than 5 days). This will allow for the completion of the study while the patient remains admitted to the hospital. The shortened duration will be utilized if the patient will be discharged before the 5-8-day window and allowing for complete data collection in the safest way possible. Thus, potentially eliminating the need to bring the patient back as an outpatient to complete the V2 in times of a pandemic or reduced visit capacity.

We propose an additional study arm to be completed in up to 5 additional patients. This arm would be an open-label study in patients with decompensated heart failure receiving treatment with IV diuretics for volume overload. The proposed arm would consist of 7

days (5-8 days to minimize missing data) of therapy with 115 mmol/day of lysine chloride. Patients enrolled into this arm will undergo identical study procedures to the randomized arm, with the exception of receiving only lysine chloride.

i.1 Study Protocol

A: Study Visit 1

1. Patient Arrival & Enrollment

- a. **Enrollment:** Patients that meet inclusion/exclusion criteria will be approached during their admission at YNHH (York St 5-1, 5-2, 5-3, 5-4, 5-7, 58 or St. Raphael's Campus Verdi 5 East and Verdi 3 East). If they agree to participate, the patient will sign an Informed Consent form prior to any study procedures taking place.

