- b. **Vital Signs, Weight and Height:** Baseline vital signs, bladder scan, weight and height are measured at the start of the study visit. Vital signs and weight measurements are repeated at the end of the study visit.
- c. **Pregnancy Testing:** A point-of-care pregnancy test is performed for women under the age of 65 who have not had a hysterectomy.
- d. **IV Line Placement & Patient Acclimation**
 - 1. **IV Line Placement:** A peripheral IV line is placed as part of the Standard of Care for receiving IV diuretics during admission at YNHH. If a suitable IV for the blood volume procedure is not available, one will be placed.
 - 2. **If a KVO is required to keep the IV line patent, Dextrose 5% fluid will be used.**
- e. **Acclimation:** Patient rests in a semi-recumbent position for approximately 60 minutes prior to undergoing blood volume determination and randomization.
- f. **Screening:** After the peripheral IV line is placed, blood will be drawn for determination of venous pH via iSTAT and/or YNHH laboratory. If the patient's venous pH is less than 7.25, they will be withdrawn from the study.
- g. **Patients will receive one of the following tracers depending on availability:**
 - 1. Iothalamate Administration
 - 1 IV iothalamate: 1 cc of Iothalamate meglumine is administered intravenously in patients without a contrast allergy
 - 2 Iohexol Administration
 - 2 IV Iohexol: 1 cc of Iohexol will be administered intravenously in patients without a contrast allergy

i. Volumex Administration and Daxor Blood Volume Sample Collection

i.1 **Baseline Blood Collection:** Blood is collected prior to the Volumex injection to establish a baseline that reflects background radiation.

i.2 **Volumex Injection:** Up to 25 microcuries of the Volumex tracer (radiolabeled albumin) is injected as an intravenous bolus (IV-push).

i.3 **Blood Volume Serial Blood Collection** A series of 5 postVolumex blood samples is collected after tracer injection, allowing for complete mixing in the bloodstream.

i.4 **Blood Volume Sample Timing:** Samples are ideally spaced ~6 minutes apart, and are collected approximately 12, 18, 24, 30 and 36 minutes after Volumex administration. Dextrose 5% fluid will be used to flush the IV line with administration of Volumex and in between blood draws for the blood volume.

- ii. **Standard YTCC or Inpatient IV Diuretic Therapy Protocol** **ii.1** The IV diuretic therapy prescribed by their treating clinician if inpatient.

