- B. What provisions are in place for management of interim results?

Given the observational nature of this study, no interim data analysis is planned.

- C. What will the multi-site process be for protocol modifications? When a protocol modification is suggested or required at any of the three clinical sites, each site will receive the proposed changes.

[figure not shown]
Modifications will be assessed for relevancy to the clinical site and for their impacts on the study design. When necessary, protocol modifications will be submitted in accordance with local IRB policy.

PI's assessment of the overall risk level if children are participating in this study? N/A

Statistical and Analytical Considerations

Endpoints: Change in blood volume over the 7-day intervention will serve as the primary endpoint. Secondary endpoints will include the change in log NTpro-BNP, serum creatinine, cystatin C, chloride and bicarbonate.

Analysis plan: A linear mixed effect model will be used to analyze the trial with class variables of time and treatment group. The mixed model will be able to accommodate the incomplete data by using all available observations. In this model, the fixed effects include the main effect of the treatment, the main effect of time, and the interaction between the them and the random effects include random intercept. Residual diagnosis for the mixed model will be performed to check whether model assumption is seriously violated. Statistical significance will be set at an alpha of 0.05. Secondary endpoints will be analyzed with the same approach.

Power and sample size: The change in blood volume in hospitalized patients undergoing several days of IV diuresis was reported by Miller and Mullan to be on average -0.7L (a 9% reduction), with a standard deviation of 1.1L .¹⁰⁷ The correlation between pre and post treatment blood volumes was high at $r=0.87$ (personal communication with [name]). Although some of this variability is driven by heterogeneity in treatment (which conducting the trial in the YTCC will address) some of it is also driven by heterogeneity in individual response to standard therapy and the relative importance of each is unknown.

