Additionally, the variability in blood volume response to lysine chloride (if one exists) is unknown. As such, given the multiple sources of variance in order to detect a 0.5L difference in change in blood volume between lysine chloride and placebo, we need to power for a standard deviation as high as 1.5L . Figure 5 illustrates that we will have an 80% power to detect an effect size $1/3$ the standard deviation with $n=100$ participants.

SECTION II: RESEARCH INVOLVING DRUGS, BIOLOGICS, RADIOTRACERS, PLACEBOS AND DEVICES

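### With complete pairs, the planned mixed model only compares mean changes in blood volume; adjusting for the pre-randomisation baseline would gain a little precision with no new data

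*Combined protocol and SAP*

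**What the plan says.** Section 4.0 defines the endpoint: "The primary endpoint will be the change in blood volume from baseline to 7 days". In the Study Visit 1 procedures, the Acclimation step reads "Patient rests in a semi-recumbent position for approximately 60 minutes prior to undergoing blood volume determination and randomization", and the first dose comes later in the same visit. The second measurement is at Study Visit 2. Section 8.2 counts two Volumex doses over the study, which confirms two blood volume measurements per patient, the first of them before randomisation.

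The Analysis plan gives a linear mixed model in which "the fixed effects include the main effect of the treatment, the main effect of time, and the interaction between the them". For the random part, it says only that "the random effects include random intercept". It adds: "The mixed model will be able to accommodate the incomplete data by using all available observations". The secondary endpoints follow the same approach. Nowhere do the documents include a baseline covariate or require the arms to share a baseline mean.

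Power and sample size cites an SD of change of 1.1 L from a published series and states "The correlation between pre and post treatment blood volumes was high at" 0.87 (a personal communication). It then plans for an SD of 1.5 L and a 0.5 L difference. The reasons given for the larger SD are that "some of it is also driven by heterogeneity in individual response to standard therapy" and that "the variability in blood volume response to lysine chloride (if one exists) is unknown". The correlation is reported but enters neither the model nor the power statement.

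**The concern.** Randomisation makes the true baseline means equal in the two arms. The treatment main effect ignores this, because it lets each arm have its own baseline mean. With two visits, complete pairs and a random intercept, the treatment-by-time term then reduces to the difference in raw mean change.

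A change score gives the baseline a coefficient of exactly 1. Estimating that coefficient from the data cannot increase the variance in large samples, and it usually lowers it. What is at stake is a small loss of efficiency in the primary test. There is no bias and no inflated error rate. The point is still worth raising because the baseline is already collected, at the cost of a radiotracer dose per patient.

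**Working it through.** **Inputs.** From Power and sample size: difference 0.5 L, SD of change 1.1 L (reported) or 1.5 L (planning), r = 0.87. From Section 4.0: 200 patients. Assumed: 1:1 allocation (100 per arm) and a two-sided 0.05 level. The documents give no visit-specific SDs. Power is by the noncentral t.

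**The plan's own figure.** The plan claims 80% power for a third of an SD with n=100. With 100 per arm, 0.5 L and 1.5 L, power is 65.0%, and 80% needs 143 per arm. The stated figure is not reproduced. That is a separate issue; 65.0% is the starting point here.

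**Equivalence.** The planned model was fitted to a simulated set of 200 complete pairs. The interaction was -0.36141 (SE 0.19258), and the difference in mean change was -0.36141 (SE 0.19258). The baseline-adjusted SE on the same data was 0.18937.

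**What subtraction already achieves (r = 0.87, equal visit SDs).**
- Visit SD = 1.1/√(2(1 − 0.87)) = 2.157 L, variance 4.654 L².
- Visit 2 alone: 4.654. Change score: 1.210 (74.0% removed). Baseline-adjusted: 4.654 × (1 − 0.87²) = 1.131 (75.7% removed).
- Adjusted over change-score variance: 1.131/1.210 = (1 + r)/2 = 0.935, a cut of 6.5%.

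**Scenario A: r = 0.87 and equal visit SDs, at either SD of change.** The factor is 0.935.

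**Scenario B: the extra variance at 1.5 L arises only at Visit 2.** This is an assumption, but it fits the plan's reasons for using 1.5 L.
- Added variance: 1.5² − 1.1² = 1.04 L². Visit 2 variance: 4.654 + 1.04 = 5.694.
- Covariance unchanged: 0.87 × 4.654 = 4.049. Visit 2/baseline SD ratio 1.106, r = 0.787.
- Adjusted variance: 5.694 − 4.049²/4.654 = 2.171. Factor: 2.171/2.250 = 0.965, a cut of 3.5%.

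| SD of change | Scenario | Power, planned → adjusted | n per arm for 80% | 95% CI half-width (L) |
|---|---|---|---|---|
| 1.1 L | A | 89.2% → 91.1% | 77 → 73 | 0.307 → 0.297 |
| 1.5 L | A | 65.0% → 67.9% | 143 → 134 | 0.418 → 0.405 |
| 1.5 L | B | 65.0% → 66.6% | 143 → 138 | 0.418 → 0.411 |

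In patients: 200 × 0.065 = 13 and 200 × 0.035 = 7. Simulation (20,000 trials each) gave 0.894 to 0.911, 0.647 to 0.676 and 0.653 to 0.669. Simulated type I error in scenario B was 0.048 for the change score and 0.047 with adjustment.

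**Sensitivity to the SD ratio.** With k = Visit 2 SD / baseline SD, the factor is (1 − r²)k²/(1 + k² − 2rk). At r = 0.87:

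| k | 0.90 | 0.95 | 1.00 | 1.05 | 1.10 | 1.149 (= 1/r) | 1.20 |
|---|---|---|---|---|---|---|---|
| Factor | 0.807 | 0.879 | 0.935 | 0.973 | 0.994 | 1.000 | 0.995 |

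If instead both visit SDs stay at 2.157 L and the SD of change is 1.5 L, then r = 1 − 2.25/(2 × 4.654) = 0.758 and the factor is 0.879.

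**A fix to avoid.** Suppose the treatment main effect is dropped but only the random intercept is kept. The model then forces equal visit variances. In scenario B the true variance is 2.207 against a model variance of 2.005. Type I error rises to 6.2% in large samples (6.4% simulated).

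**The case against.** The strongest reply is that nothing is broken. The endpoint is change, the planned contrast estimates it directly and without bias, and subtraction already removes most of the variance. At the planning SD, scenario B moves power by 1.6 points and the interval half-width by 0.007 L, which would alter no decision. This stands, and it is why the point is a recommendation about efficiency only.

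The size also rests on an SD ratio that the documents do not give. Scenario B starts from a ratio of exactly 1. Adding the same 1.04 L² from a starting ratio of 1.05 gives a cut of 1.5%, and from 1.10 only 0.3%; from 0.95 it gives 6.5%. Variable Visit 2 timing could add further variance at that visit. This stands too: 7 to 13 patients describes two plausible cases and is not a bound.

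Scenario A at 1.5 L is the less natural of the two, since it implies a visit SD of 1.5/√0.26 = 2.94 L against 2.16 L at 1.1 L. Scenario B is the better guide at the planning SD.

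Finally, the mixed model was chosen for incomplete data, where the exact equality no longer holds. With 5% to 20% of Visit 2 values missing at random, however, its variance is only 0.3% to 2.4% below that of the complete-case change score. That gain comes from unpaired baselines, which the model recommended below also keeps.

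**Conclusion.** The concern holds for blood volume. With complete pairs, the planned primary test is the comparison of raw mean changes, and it makes no use of the equality of baseline means that randomisation guarantees. The remaining loss is small: a variance cut of 6.5% or 3.5% forgone in the two cases closest to the documents. In large samples adjustment never does worse, but the gain vanishes at r = 0.87 if the Visit 2 SD is about 1.15 times the baseline SD. It is larger if the Visit 2 SD is the smaller one.

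These figures assume 100 per arm, a two-sided test and the unpublished correlation of 0.87. If n=100 means 50 per arm, power goes from 61.4% to 64.3% at 1.1 L, and from 37.9% to 40.0% (scenario A) or 39.0% (scenario B) at 1.5 L. Adjustment does not close the gap to 80% power.

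**What to change.** Amend the Analysis plan before unblinding:

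- **Primary test.** In randomised patients, use the Visit 2 treatment contrast from a mixed model with time and treatment-by-time but no treatment main effect, so that the arms share one baseline mean.
- **Covariance.** State an unstructured covariance for the two visits. The random intercept alone should not be kept in this model, because of the type I error shown above.

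This model keeps patients who have only a baseline value, as the plan intends. Analysis of covariance of Visit 2 blood volume (or of change) on Visit 1 blood volume is an acceptable equivalent for complete pairs. Both versions give the same treatment effect, so the endpoint definition need not change.

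Use the same model for secondary endpoints whose baseline sample precedes the first dose. If safety-visit laboratory values enter those models, name the Visit 2 contrast as the test. The gain for these endpoints has not been quantified.

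The cost is two sentences in an amendment, with any ethics submission it requires. No new data are needed.

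### The stated 80% power for a 0.5 L difference (1/3 SD) is wrong: the two-arm design gives about 65% with 200 patients and about 38% with 100

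*Combined protocol and SAP*

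**What the plan says.** Section 4.0 (Study Design) describes a "randomized, double blind, placebo controlled study of 200 patients with decompensated heart failure", with parallel-group randomization to lysine chloride or placebo. Section 12.2 (Targeted Enrollment) repeats 200.

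Under Statistical and Analytical Considerations, the primary endpoint is the change in blood volume, and "Statistical significance will be set at an alpha of 0.05". The analysis is a mixed model with treatment, time, their interaction and a random intercept. The Power and sample size paragraph starts from a published mean change in hospitalized patients on IV diuretics, "with a standard deviation of 1.1L", and a pre/post correlation of 0.87. The stated aim is a sample size chosen "in order to detect a 0.5L difference in change in blood volume between lysine chloride and placebo". Because several sources of spread are unknown, the paragraph sets the planning value above the published one: "we need to power for a standard deviation as high as 1.5L". It concludes, citing Figure 5, that "we will have an 80% power to detect an effect size $1/3$ the standard deviation with $n=100$ participants".

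The plan does not say whether n=100 is a total or a number per arm. Nor does it state the sidedness of the test, the allocation ratio or any allowance for dropout.

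On variability, the same paragraph says that "some of this variability is driven by heterogeneity in treatment (which conducting the trial in the YTCC will address". In section 4.0, however, the diuretic step of Study Visit 1 reads "The IV diuretic therapy prescribed by their treating clinician if inpatient".

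**The concern.** The ratio 0.5/1.5 is exactly the quoted 1/3 SD, so the effect size is not in doubt. What does not fit is 80% power for that effect with 100 participants in a comparison of two independent groups. Nor is it clear how n=100 relates to the 200 patients planned.

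This is the only power statement for the primary endpoint. A reader would infer a 20% chance of missing a true 0.5 L effect at the SD the plan says it must allow for. If the real chance is much higher, a null result could be over-read as evidence against a 0.5 L effect.

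**Working it through.** **Inputs from the plan.** Difference δ = 0.5 L; SD of change σ = 1.5 L; alpha 0.05; parallel groups; 200 randomized. The 1.5 L is an SD of change: it is an inflation of the 1.1 L that the plan gives as the SD of the change.

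**Assumptions, because the plan is silent.** Two-sided test, 1:1 allocation, no dropout. With two time points and complete data, the treatment-by-time interaction in the planned model is the between-arm difference in mean change, so two-sample power applies.

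**Trying to reproduce 80%.** By normal approximation with n per arm, power = Φ(δ / (σ√(2/n)) − 1.960).

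- 100 in total, n = 50: 1.5 × √(2/50) = 0.300; 0.5/0.300 = 1.667; Φ(−0.293) = 38.5%. Noncentral t: 37.9%.
- 100 per arm, n = 100: 1.5 × √(2/100) = 0.2121; 0.5/0.2121 = 2.357; Φ(0.397) = 65.4%. Noncentral t: 65.0%.

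The shortfall from 80% is about 15 points on the generous reading and about 42 on the other.

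**Sample size for 80%.** n per arm = 2 × (1.960 + 0.842)² / (1/3)² = 2 × 7.85 × 9 ≈ 141.3, so 142. The t calculation gives 143 per arm, 286 in total.

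**What 200 patients can support.**

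- Detectable difference at 80% power: 0.398 SD × 1.5 L = 0.60 L (t calculation).
- Largest SD giving 80% at 0.5 L: 0.5/0.398 = 1.26 L.
- At the cited SD of 1.1 L: 1.1 × √(2/100) = 0.1556; 0.5/0.1556 = 3.214; Φ(1.254) ≈ 89%. With 100 in total, power at 1.1 L is 61% (t).

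**Other readings tried at 1/3 SD.**

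| Reading | 100 total | 200 total |
|---|---|---|
| One-sided 0.05 (t) | 50.4% | 75.9% |
| Baseline-adjusted, r = 0.87, two-sided (normal) | 40.7% | 68.3% |
| Baseline-adjusted and one-sided (normal) | 53.1% | 78.6% |
| 1.5 L as a single-time-point SD (change SD 0.765 L), two-sided (normal) | 90.5% | 99.6% |
| 2:1 allocation, two-sided (normal) | 34.9% | 60.3% |

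Baseline adjustment multiplies the variance by (1 + 0.87)/2 = 0.935. The change SD of 0.765 L is 1.5 × √(2 × (1 − 0.87)). A one-sample test with n = 100 gives 91.0% (t), but that is not this design.

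**Setting.** Section 1.0 calls this an inpatient study, and sections 4.0 and 7.1 recruit from named inpatient floors. Section 3.0 itself describes therapy in hospitalized patients as highly heterogeneous. The reassurance drawn from YTCC care does not match that enrolment.

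**The case against.** Several points can be made for the plan.

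- **Sidedness and allocation are not stated.** A one-sided 0.05 test would narrow the gap to 76% against 80% with 200 patients. That is right as arithmetic, and the 65% does rest on a two-sided test and 1:1 allocation. Both are the usual conventions, nothing in the plan indicates a one-sided test, and unequal allocation lowers power.
- **One combination comes close.** A one-sided test, baseline adjustment and 100 per arm together give 78.6%. The plan specifies neither the one-sided test nor the adjustment, so this does not support the figure.
- **Figure 5 is not available.** Its settings cannot be checked, but the 80% claim stands in the text and can be tested from the text.
- **The 1.5 L is a ceiling.** At 1.1 L, 200 patients give 89%. This stands, and it means the design is not poor in itself. The error is in the power claimed at 1.5 L.
- **The 100-patient case is not the planned trial.** Sections 4.0 and 12.2 both give 200, so 65% is the figure that matters. Section 2.0, however, gives 5 years at 25 patients per year, 5 × 25 = 125. At that size power would be about 46%, so the enrolment figures need reconciling.
- **The YTCC is mentioned elsewhere.** The Visit 1 diuretic heading and section 11.6 refer to it, and section 8.2 allows for patients who are not inpatients. The description of the setting is therefore mixed. The remark also has no effect on the calculation, since the planning SD was raised, not lowered. This part is secondary.

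**Conclusion.** The concern holds. On the plan's own difference, SD and alpha, power is 65.0% with 200 patients and 37.9% with 100, not 80%. These figures assume a two-sided test, 1:1 allocation and no dropout; missing second blood-volume measurements would lower them. No reading that the documents support gives 80%. If the SD of change really is 1.5 L, a true 0.5 L effect would be missed about 35% of the time with 200 patients (about 62% with 100), against the 20% implied. The YTCC remark is a lesser inconsistency with no numerical effect.

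**What to change.** Keep 200 patients and rewrite the end of the Power and sample size paragraph, for example:

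*With 100 patients per arm (200 in total, 1:1), two-sided alpha 0.05 and an SD of change of 1.5 L, power to detect a 0.5 L difference is 65%. Power of 80% is reached at a difference of 0.60 L, or at 0.5 L if the SD is 1.26 L or less. At an SD of 1.1 L, power is 89%.*

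The sponsor should confirm the two-sided test and 1:1 allocation when adopting this text, bring Figure 5 into line with it, and reconcile the accrual rate in section 2.0 with 200. Delete the statement that the YTCC setting will address treatment heterogeneity.

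The cost is protocol and SAP wording only. The stated power becomes less favourable; no patients, procedures or analyses are added.
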